Date: February 1st, 2022

Study Protocol and Statistical Analysis Plan

Study Title	A Novel, Non-pharmacological, Intervention for the Management of ADHD in Adolescents
Protocol ID	VIZO_004
ClinicalTrials.gov ID	NCT05835336

Protocol Synopsis

Device Name	VIZO Glasses
Objectives	To Assess the Efficacy and Safety of a Novel Device (VIZO Glasses) in the Management of ADHD in Adolescents.
Study Group Investigational Group	VIZO Glasses: Eyeglasses with personalized peripheral retinal stimuli
Key Eligibility Criteria	
Inclusion Criteria	
 • Documented history of primary ADHD diagnosis by certified clinicians • Age 12-17 y • Minimum total of 24 on the parent ADHD-IV Rating Scale (ADHD-RS) • Written informed consent • Able and willing to complete all required ratings and assessments
Exclusion Criteria	
 • Any current psychiatric/neurological comorbidity (e.g., epilepsy, Autism, depression, TBI, etc.), other than ADHD • ADHD Medications (stimulants, non-stimulants, other) • Undergoing Neurofeedback, cognitive training • Any other reason that, in the opinion of the investigator, prevents the participant from participating in the study
Endpoints	
Primary	
Primary Outcome Measure: Change in the ADHD Rating Scale (ADHD-RS) Parent-report Questionnaire - Total Score [Time Frame: Baseline, 2-month]
 
The ADHD-RS is a parent report questionnaire that is used to aid in the diagnosis of ADHD in children ranging from ages 5-17. The questionnaire contains 18 symptom items corresponding to the DSM-V criteria for ADHD. The parent rates each symptom item on a 4-point Likert scale ranging from 0 ('Never or Rarely') to 3 ('Very Often'). The total score goes from 0 up to 54. Higher scores mean more symptoms and higher ADHD impairments.
 
Change in the ADHD Rating Scale (ADHD-RS) Parent-report Questionnaire - Inattention Subscale [Time Frame: Baseline, 2-month]
 
The Inattention subscale of the ADHD-RS contains 9 symptom

Protocol Synopsis

	
items, that are designed to measure the child's attention level on tasks or play activities. The items are rated by the parent on a 4-point Likert scale ranging from 0 ('Never or Rarely') to 3 ('Very Often'). The total score goes from 0 up to 27. Higher scores mean more symptoms and higher ADHD impairments.
 
Change in the ADHD Rating Scale (ADHD-RS) Parent-report Questionnaire - Hyperactivity-Impulsivity Subscale [Time Frame: Baseline, 2-month]
 
The Hyperactivity-Impulsivity subscale of the ADHD-RS contains 9 symptom items, that are designed to measure the child's hyperactivity level and impulsivity level. The items are rated by the parent on a 4-point Likert scale ranging from 0 ('Never or Rarely') to 3 ('Very Often'). The total score goes from 0 up to 27. Higher scores mean more symptoms and higher ADHD impairments.
 
Change in Behavior Rating Inventory of Executive Function (BRIEF) - Metacognitive Index [Time Frame: Baseline, 2-month]
 
The Metacognition Index (MI) of the BRIEF reflects a child's ability to self-manage and monitor tasks cognitively. The subscale is composed of the Initiate, Working Memory, Plan/Organize, Organization of Materials, and Monitor scales of the BRIEF. It uses a Likert-type response format ranging from 1 to 3, where 1 is never, 2 is sometimes, and 3 is often. High scores indicate executive deficit.

Secondary	
Secondary Outcome Measures:
 
Clinical Global Impression-Improvement (CGI-I) [Time Frame: 2-month]
 
Based on an interview with the participant, the clinician rates the total improvement on a 7 point scale as follows: 1=very much improved since the initiation of treatment; 2=much improved; 3=minimally improved; 4=no change from baseline (the initiation of treatment); 5=minimally worse; 6= much worse; 7=very much worse since the initiation of treatment.
 
Change in Behavior Rating Inventory of Executive Function (BRIEF) - Global Executive Composite [Time Frame: Baseline, 2-month]
 
The BRIEF is a standardized measure that captures views of

Protocol Synopsis

	executive functions or self-regulation in the everyday environment. The BRIEF is composed of 86 items, where each item is rated by the parent, using a 3-point Likert scale ranging from 1 ('Never') to 3 ('Often'). The Global Executive Composite (GEC) is an overarching summary score that incorporates all of the BRIEF clinical scales. High scores indicate executive deficit.
Other Outcomes	Adverse events will be monitored and documented.
Follow-up Visits Schedule	This was a two-month, open-label study in which eligible ADHD-diagnosed adolescents were provided with a pair of VIZO-Glasses featuring a personalized visual stimuli pattern for each participant. A baseline assessment of the participants' ADHD clinical profile pre-intervention included the ADHD-RS and the Behavior Rating Inventory of Executive Function (BRIEF) questionnaires. In addition, participants completed the Conners' Continuous Performance Test-3 (CPT-3). Optical centration parameters and demographic information were collected for each participant. Participants were then invited to complete a personalization process in which they were fitted with personalized VIZO-glasses. Participants were instructed to wear their Vizo-glasses for at least two hours daily for two months. A follow-up assessment at the end of the intervention re-assessed ADHD performance on the ADHD-RS and BRIEF questionnaires. In addition, participants completed the CPT-3 test while wearing their VIZO-glasses. The Clinical Global Impression-Improvement (CGI-I) rating scale was administered by a clinician.
Sample Size	Given the exploratory nature of the study, the sample size was chosen to be sufficiently large to detect significant within subject effects of at least 0.5 (Cohen's D) for a 2-Tailed test, at $\alpha=0.05$ with a power of 80%.
Analysis Plan	Paired samples t-tests will be used to test the effect of the VIZO-glasses intervention, comparing the baseline and end-of-intervention performances. No corrections for multiple testing will be applied due to the exploratory nature of the study. The safety analysis will include all available data on the intent-to-treat (ITT) population.

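### The Analysis Plan treats a single-arm, open-label, parent-rated pre-post change as a test of the device's effect, which this design cannot isolate

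*Combined protocol and SAP*

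**What the plan says.** All references are to the combined protocol and SAP.

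- **Analysis Plan:** "Paired samples t-tests will be used to test the effect of the VIZO-glasses intervention, comparing the baseline and end-of-intervention performances". The Objectives row gives the aim as assessing the efficacy and safety of the glasses in adolescents with ADHD.
- **Study Group and Follow-up Visits Schedule:** only an investigational group is listed. "This was a two-month, open-label study in which eligible ADHD-diagnosed adolescents were provided with a pair of VIZO-Glasses".
- **Endpoints, Primary:** four measures: ADHD-RS Total, its two subscales, and the BRIEF Metacognition Index. The first is "Change in the ADHD Rating Scale (ADHD-RS) Parent-report Questionnaire - Total Score [Time Frame: Baseline, 2-month". On the ADHD-RS, "The parent rates each symptom item on a 4-point Likert scale"; the description of the BRIEF under Secondary says that its items are also rated by the parent.
- **Inclusion Criteria:** "Minimum total of 24 on the parent ADHD-IV Rating Scale (ADHD-RS". This is the scale of the first primary measure.
- **Follow-up Visits Schedule:** the assessment of the "ADHD clinical profile pre-intervention included the ADHD-RS and the Behavior Rating Inventory of Executive Function (BRIEF) questionnaires". It is the only pre-intervention ADHD-RS described, and nothing says whether it is the rating used for entry.
- **Exploratory label:** it appears twice, for the sample size ("Given the exploratory nature of the study, the sample size was chosen to be sufficiently large to detect significant within subject effects") and for multiplicity ("No corrections for multiple testing will be applied due to the exploratory nature of the study").

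No section mentions expectancy, change over time or regression to the mean.

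**The concern.** The null hypothesis of a paired t-test is that the mean change is zero. Rejecting it says that scores moved, not why. Here the raters are parents who know that their child has the glasses, and no comparator shows what would have happened without them. The plan nevertheless calls the test one of the intervention's effect, under an efficacy objective. Read as written, a significant fall in ADHD-RS or BRIEF scores could be reported as device efficacy.

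The entry cut-off may add to this. If the score that admits a participant is also the score from which change is measured, selecting on a high value produces some average fall on re-rating even with an inert device. That bias favours the device, and nothing in the analysis subtracts it.

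**Working it through.** **1. What the test can identify (no assumed figures).** The mean observed change is the sum of the device effect, parent expectancy, change over time and, if the entry rating is the baseline, regression to the mean. One open-label arm gives one estimate of that sum. The t-test asks whether the sum is zero, and no other planned analysis separates its parts.

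**2. Number of pairs implied by the plan.** The plan states d = 0.5, two-sided 5% and 80% power, but prints no N, so there is no figure to reproduce. The normal approximation gives ((1.960 + 0.842)/0.5)² = 31.4, so 32. The exact noncentral t gives 34 pairs (power 80.8%; 33 pairs give 79.5%). With 33 df the critical t is 2.035, so the smallest significant standardised change (dz) is 2.035/√34 = 0.349.

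**3. Expectancy or change over time.** The documents give no size. For assumed non-device changes of dz 0.2, 0.3 and 0.5, 34 pairs give a significant improvement in about 20%, 40% and 81% of trials. The last is simply the planned power: the test is as sensitive to a non-device change as to a device effect of the same size.

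**4. Selection, only if one rating serves as both entry score and baseline.** From the documents: cut-off 24, scale 0 to 54. Assumed: mean μ and SD σ of the candidates rated, retest correlation r, normal scores, no device effect.

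- c = (24 − μ)/σ; λ = φ(c)/(1 − Φ(c))
- expected fall = (1 − r)σλ
- Var(change) = (1 − r)²σ²(1 + cλ − λ²) + σ²(1 − r²)
- dz = fall/SD(change); chance = upper tail of the noncentral t, 33 df, noncentrality dz√34

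Example, μ = 28, σ = 10, r = 0.8: c = −0.4 and λ = 0.562. The fall is 0.2 × 10 × 0.562 = 1.12 points. The variance is 0.04 × 45.95 + 100 × 0.36 = 37.84, so the SD is 6.15. Then dz = 0.18 and the chance is 17.7%, against 2.5%.

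| Mean, SD | Excluded by cut-off | Fall in points, r 0.9 to 0.6 | dz | Chance of significant improvement |
|---|---|---|---|---|
| 20, 10 | 66% | 1.07 to 4.28 | 0.24 to 0.52 | 28% to 83% |
| 24, 10 | 50% | 0.80 to 3.19 | 0.18 to 0.38 | 18% to 58% |
| 28, 10 | 34% | 0.56 to 2.25 | 0.13 to 0.27 | 11% to 33% |
| 32, 10 | 21% | 0.37 to 1.47 | 0.08 to 0.17 | 7% to 16% |
| 36, 10 | 12% | 0.22 to 0.88 | 0.05 to 0.10 | 4.6% to 8.3% |
| 40, 8 | 2.3% | 0.04 to 0.18 | 0.01 to 0.03 | 2.9% to 3.5% |

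The top row is not a ceiling: mean 20, SD 8, r 0.6 gives dz 0.55 and 88%. The normal model ignores the scale limits; a check with integer scores bounded at 0 and 54 gave 1.08 points and 16.4% for the worked example.

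**5. Reach across the endpoints.** The cut-off acts directly on the ADHD-RS Total. If both subscales share the fall equally, each takes half (1.12/2 = 0.56 points in the example). No BRIEF cut-off is stated, so the BRIEF is affected only through its correlation with the entry score: a fall of (ρ1 − ρ2)λ SD units, where ρ1 and ρ2 are its correlations with that score at baseline and month 2. This is zero if they are equal; a drop of 0.12 gives 0.12 × 0.562 = 0.067 SD.

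**The case against.** **The design is disclosed.** The plan says open-label, sizes the study for within-subject effects, and explains in the same sentence that the effect is a baseline to end-of-intervention contrast. It claims no superiority over a control and does not say how a positive result will be reported. This stands as mitigation. It does not remove the word effect, or the efficacy objective.

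**The study is called exploratory.** The phrase describes the whole study and softens the efficacy reading. But the plan uses it only to justify the sample size and the absence of multiplicity correction, never to limit attribution.

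**Not every measure is parent-rated.** True, but the CGI-I is a secondary clinician rating from an interview with the participant, with no blinded rater described. The CPT-3 is collected but not listed as an endpoint. Neither supplies a comparator.

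**The selection figures rest on assumptions.** This stands in full. A reader might infer that the entry rating is the baseline and that part of any fall is therefore known to be artefact; the documents neither confirm nor exclude this. A reader might equally infer that the artefact is too small to produce significance by itself. That is not supported either: with SD 10 and r 0.6, a mean of 24 or 20 gives dz 0.38 or 0.52, above the 0.349 threshold.

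**Conclusion.** The point holds. The plan states an inference that one open-label arm with parent-rated primary measures cannot give. This rests on the text alone and needs no assumed figure. It should be fixed, because it governs what may be concluded from a positive result and the remedy is almost free.

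The selection part is conditional on one rating serving both purposes. Its direction would favour the device. Its size is undetermined: about 3% to 83% significant improvement against 2.5% across the tabulated scenarios, and close to nominal if few candidates score near 24. The weight of the point does not depend on these rates.

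A reader might go further and infer that the glasses do not work, or that a single-arm study is illegitimate here. The documents support neither. A single-arm exploratory study is a defensible choice, and its data remain usable as a description of change.

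**What to change.** **1. Reword the claim.** Suggested Analysis Plan text: *Paired t-tests estimate the open-label within-subject change from baseline to 2 months. Without a control arm this change may include parent expectancy, change over time and regression to the mean, and it will not be reported as efficacy attributable to the glasses.* Apply this to all ADHD-RS and BRIEF endpoints, and apply the same limit on attribution to the CGI-I. Align the Objectives row, so that it does not promise efficacy while the analysis disclaims it. This works even if enrolment is over. The cost is wording, and a weaker claim from a positive result.

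**2. State whether the entry ADHD-RS is the baseline.** This is one sentence. If it is the baseline and enrolment is still open, use the first rating for eligibility only, and measure change from a repeat parent rating taken before the glasses are handed over, with no cut-off applied. This reduces the selection part but may not remove it. With mean 28 and SD 10, if the first rating correlates 0.9 with the repeat and 0.8 with month 2, (0.9 − 0.8) × 10 × 0.562 = 0.56 of the 1.12 points remains. It does nothing about expectancy. The cost is one extra 18-item parent form, which may have to be sent separately because the plan does not say that a parent attends the personalization step. The Follow-up Visits Schedule is written in the past tense; if enrolment has closed, the repeat rating is moot, but the statement and item 1 still apply. Neither item needs more participants.

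### Does leaving the CPT-3 out of every outcome list, with no named score, require a change to the plan?

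*Combined protocol and SAP*

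**What the plan says.** The combined protocol and SAP mentions the CPT-3 only in the Follow-up Visits Schedule. The participants' "ADHD clinical profile pre-intervention included the ADHD-RS and the Behavior Rating Inventory of Executive Function (BRIEF) questionnaires", and the CPT-3 was completed at that same assessment. Fitting came afterwards: "Participants were then invited to complete a personalization process in which they were fitted with personalized VIZO-glasses". Wear was then set as follows: "Participants were instructed to wear their Vizo-glasses for at least two hours daily for two months". At the end of the intervention the ADHD-RS and BRIEF were repeated, and for the CPT-3 the text reads "In addition, participants completed the CPT-3 test while wearing their VIZO-glasses".

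The Endpoints section lists four primary measures (ADHD-RS total, its inattention and hyperactivity-impulsivity subscales, and the BRIEF Metacognitive Index) and two secondary ones (CGI-I and the BRIEF Global Executive Composite). Other Outcomes covers adverse events only. The Analysis Plan applies paired t-tests to baseline against end of intervention without naming any instrument, and declines multiplicity correction because the study is exploratory.

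**The concern.** The study is open-label with one group, and every listed efficacy endpoint is a rating by someone who knows the adolescent is using the device. The CPT-3 is the only efficacy measure taken from a task. A measure collected twice but given no outcome status could be dropped if it shows nothing, or brought forward through whichever score looks best.

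The second worry is interpretation. The baseline test came before fitting and the follow-up test was done with the glasses on. A change could therefore come from wearing the lenses during the test, from two months of use, from practice, or from expectancy. No glasses-off test at two months is described, so a reader might take the change for a sustained effect that the design cannot isolate.

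**Working it through.** **1. Where the CPT-3 stands.** Reading all three outcome lists against the schedule:

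| Instrument | In the schedule | In an outcome list | Source of the data |
|---|---|---|---|
| ADHD-RS (total and two subscales) | baseline, end | primary (3) | parent |
| BRIEF Metacognitive Index | baseline, end | primary (1) | parent |
| BRIEF Global Executive Composite | baseline, end | secondary (1) | parent |
| CGI-I | end | secondary (1) | clinician |
| CPT-3 | baseline, end (glasses on) | none | task |

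Listed efficacy endpoints: 4 + 2 = 6, of which 5 are parent-rated, 1 clinician-rated and 0 task-based. The omission is real. It is not an artefact of text extraction, because all three lists are present.

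**2. Whether a contrast is missing.** The schedule gives both occasions, places fitting after baseline, and states that the glasses were on at follow-up. The Analysis Plan gives a paired comparison of baseline with end of intervention, and its wording is general enough to take in the CPT-3. Put together, the contrast is two months with glasses on against the pre-fitting baseline. That baseline was done without the study glasses is an inference from the order of events; the text does not state it. What is absent is an outcome status and a named score.

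**3. What free choice of score could cost.** The documents give no number of CPT-3 scores, so the count k is an assumption. With a two-sided 0.05 test, the chance of a false significant result in the direction of improvement is 0.05 / 2 = 0.025 per score. With no true change in any score and independence, the chance of at least one is 1 − 0.975^k:

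- k = 1: 2.5%, so no excess
- k = 3: 1 − 0.975³ = 7.3%
- k = 9: 1 − 0.975⁹ = 20.4%

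If the scores correlate at 0.5 (also assumed), simulation of 40,000 trials with 34 pairs gives about 6% for k = 3 and 14% for k = 9. The plan states no sample size; 34 complete pairs is what its inputs imply (d = 0.5, two-sided 0.05, 80% power): a paired t-test has power 0.808 with 34 pairs and 0.795 with 33. The independent-score figures do not depend on the sample size.

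**4. What naming a score would gain.** It removes the excess over 2.5% only if several scores exist, the best would otherwise have been picked, and the follow-up data are still unseen. The schedule is written in the past tense, so the last condition may fail; the most that could then be done is to label the analysis post hoc. Naming a score does nothing about practice, time or expectancy. If the named score is tested, it also adds one more uncorrected test. Assuming independence, the chance of any false positive among the five listed change endpoints is 1 − 0.95⁵ = 22.6%, and with one CPT-3 score added it is 1 − 0.95⁶ = 26.5%.

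**The case for a change.** The strongest case for acting is that calling a study exploratory can excuse uncorrected testing but does not excuse leaving a collected measure without a status. Each of the other efficacy instruments in the schedule appears in an outcome list with a time frame; the CPT-3 alone does not. It is also the one measure that does not pass through a parent or clinician, so selective use of it would be tempting in either direction. The remedy would be a few words and no extra visit.

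The factual part stands: the CPT-3 has no listed status and no score. The consequence is weaker. The task removes the rater but not the participant's expectancy or effort, so it could supplement the ratings but not validate them. Both feared outcomes, omission and selection, are possibilities that attach to any unlisted assessment; nothing in the documents announces either. The daily wear instruction sets a minimum, so it does not show how long the glasses were off, and the plan claims no glasses-off effect. The suggestion to fix one score does not say which score, so it offers no better method than a competent analyst would adopt anyway.

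**Conclusion.** No change to the plan follows. The gap is genuine but small: one supplementary test, collected twice, lacks a stated outcome status and a named score. Following the plan as written gives no wrong result for any of the six listed efficacy endpoints, and the documents make no CPT-3 claim that would need correcting.

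The possible cost runs from nothing, if one score is used, to a 20% chance of a false improvement, if nine independent scores are examined and the best is reported. That upper figure rests on an assumed number of scores, independence, no true change in any of them, and deliberate selection. None of these comes from the documents.

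A sensible analyst will treat the CPT-3 as exploratory, say which scores were examined, report the result whatever its direction, and describe it as a glasses-on change from the pre-fitting baseline. Read that way, it supports no claim to separate the immediate effect of the lenses from two months of use, practice or expectancy.

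### Does CPT-3 need a glasses-off run at two months, given that baseline was taken before fitting and follow-up with the glasses on?

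*Combined protocol and SAP*

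**What the plan says.** All the relevant text is in the Protocol Synopsis of the combined protocol and SAP.

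- **Baseline (Follow-up Visits Schedule).** The assessment of the "ADHD clinical profile pre-intervention included the ADHD-RS" and the BRIEF, and participants also took the "Continuous Performance Test-3 (CPT-3"). Fitting comes next: "Participants were then invited to complete a personalization process in which they were fitted with personalized VIZO-glasses".
- **Exposure.** "Participants were instructed to wear their Vizo-glasses for at least two hours daily for two months".
- **Two months.** The questionnaires are repeated, and for the performance test: "In addition, participants completed the CPT-3 test while wearing their VIZO-glasses". No run without the glasses is described at this visit, and no run with them at baseline.
- **Design.** "This was a two-month, open-label study", with one group.
- **Endpoints.** CPT-3 is not among the primary, secondary or other outcomes. The listed efficacy outcomes are the ADHD-RS, the BRIEF indices and the CGI-I.
- **Sample Size.** The section opens "Given the exploratory nature of the study" and describes a sample "sufficiently large to detect significant within subject effects of at least 0.5" (Cohen's d), two-tailed, at alpha 0.05 with 80% power. It states no N.
- **Analysis Plan.** Paired t-tests compare baseline with end of intervention. No instrument is named.

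**The concern.** The two CPT-3 runs differ in more than time. That baseline was done without the glasses is an inference from the order of events, but a safe one, since the personalised pair had not yet been fitted. At two months the glasses are on. A change could therefore be an effect that exists only during wear, something that has built up over two months and remains when the glasses come off, or practice and the passage of time. The data give one contrast for all of these.

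The distinction is of interest for two reasons. First, instructed wear is a minimum of two hours a day. If the waking day is 14 to 16 hours (an assumption), a participant at that minimum spends (14 − 2)/14 = 86% to (16 − 2)/16 = 88% of it without the glasses. A test taken with them on does not speak to those hours. Second, CPT-3 is the only performance test in an open-label study whose listed efficacy outcomes are all ratings, so a reader may give it particular weight. The natural suggestion is a glasses-off run at the two-month visit, in randomised order with the glasses-on run.

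**Working it through.** **What the present design can estimate.** Let T be time, practice and regression to the mean, L an effect that lasts without the glasses, and W an effect present only while wearing. The sole CPT-3 contrast is

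(two months, on) − (baseline) = T + L + W.

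That is one equation in three unknowns, so none of T, L, W or T + L is estimable separately. The share due to wearing, W/(T + L + W), has no bounds, because the terms may differ in sign. With W = +0.4 and T + L = −0.1 it is 0.4/0.3 = 133%. With W = −0.1 and T + L = +0.5 it is −0.1/0.4 = −25%. These values are illustrative only.

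**What a glasses-off run would add.** On minus off at two months estimates W. Off minus baseline estimates T + L, but T and L stay inseparable without a control group.

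**Precision of the added run.** The documents give no N, so there is no stated figure to reproduce. Their inputs imply one:

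- Normal approximation: (1.960 + 0.842)²/0.5² = 31.4, so 32.
- Exact paired t (noncentral t): power 0.795 at n = 33 and 0.808 at n = 34, so 34.

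Assume 34 complete pairs, and express differences in SD of the on-off difference. The 95% CI half-width is t(0.975, 33)/√34 = 0.349. Power by true on-off effect:

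| True effect (SD) | 0.50 | 0.40 | 0.30 | 0.25 |
|---|---|---|---|---|
| Power | 81% | 62% | 40% | 29% |

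**Order and carry-over.** Let w be the true on-off effect, p the gain from being the second run of the day, and c the benefit carried from an on-first run into the off run that follows. Then

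- on-first: on − off = w − p − c
- off-first: on − off = w + p
- mean of the two order means = w − c/2.

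Randomising and modelling order removes p but leaves a bias of −c/2. Simulation with 17 per order, 100,000 trials and w = 0.50 gave the same results for p = 0.2 and p = 0.4 (p and c are assumed values):

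| Carry-over c (SD) | Bias | CI coverage | Power |
|---|---|---|---|
| 0 | 0.00 | 95% | 81% |
| 0.1 | −0.05 | 94% | 72% |
| 0.2 | −0.10 | 91% | 62% |
| 0.3 | −0.15 | 86% | 51% |

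A check free of carry-over would compare first runs only, 17 against 17. Its half-width is t(0.975, 32) × √(2/17) = 0.70 SD of the score. Adjusting for baseline CPT-3, with an assumed correlation of 0.5 to 0.8, brings this to between 0.61 and 0.42.

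**Effect on the comparison already in place.** For the off-first half, the glasses-on run becomes the third CPT-3 exposure instead of the second. Presenting change from baseline by order leaves 17 per group, with half-width t(0.975, 16)/√17 = 0.51 SD of the change.

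**The case for a change.** The best case for acting is that the confounding is real, no analysis of the existing data can undo it, and a remedy looks cheap: one more run of a test already in use at an existing visit or, if visits are over, one line of wording. The Analysis Plan does not exclude a CPT-3 paired test and says nothing on how to read one.

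The identification argument stands in full. The step from there to a change does not.

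- The objective is the efficacy and safety of the device in managing ADHD. An effect that needs the glasses on and one that outlasts them are both device effects under that objective. Separating them is a further, mechanistic aim, which a study describing itself as exploratory may fairly leave out.
- It is not clear that CPT-3 will be tested at all. The Analysis Plan refers to performance without naming instruments, and the Follow-up Visits Schedule uses the same noun for the ADHD-RS and BRIEF.
- The added run is not free. It alters the glasses-on measurement for half the participants, it is unmasked, and it understates the effect if benefit carries over.
- The visits are described in the past tense. The future tense used for analysis and adverse events leaves some doubt, but the run is probably moot.
- A reporting label would mostly repeat a test condition that the document already states. The remainder of such a label, that time and practice are uncontrolled, is the single-arm limitation shared by every paired test here.

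**Conclusion.** The observation is correct and no change to the plan follows. The CPT-3 change compares performance with the glasses on at two months with performance before fitting. The part that depends on wearing is not identified, and it cannot support a claim of improvement that persists without the glasses. The documents make no such claim. An analyst who does report CPT-3 has the test conditions in the text and would ordinarily state them with the result.

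No listed endpoint, test or sample-size input is affected, so the numerical consequence for the planned results is nil. A glasses-off run is an optional design choice with its own costs: useful power only for an on-off difference near 0.50 SD, a bias of half of any carry-over, and a disturbed baseline comparison for half the sample. Those figures rest on an assumed 34 complete pairs and on assumed order and carry-over effects. The conclusion rests on none of them. It depends on CPT-3 lying outside the listed outcomes and on the stated objective not distinguishing effects during wear from lasting ones.

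### Does the plan have to change because the only efficacy test it names cannot be applied to the CGI-I, a single 2-month rating?

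*Combined protocol and SAP*

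**What the plan says.** In the combined protocol and SAP, the Analysis Plan gives one sentence on efficacy testing: "Paired samples t-tests will be used to test the effect of the VIZO-glasses intervention, comparing the baseline and end-of-intervention performances". It then declines multiplicity correction because the study is exploratory, and says which population the safety analysis uses.

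Under Endpoints, Secondary, the CGI-I carries a single time point: "Clinical Global Impression-Improvement (CGI-I) [Time Frame: 2-month". A clinician rates it on seven ordered categories. Three of them denote improvement: "1=very much improved since the initiation of treatment; 2=much improved; 3=minimally improved". The neutral category is "4=no change from baseline (the initiation of treatment"; categories 5 to 7 denote worsening.

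The Follow-up Visits Schedule is consistent with this. Before the intervention, "A baseline assessment of the participants' ADHD clinical profile pre-intervention included the ADHD-RS and the Behavior Rating Inventory of Executive Function (BRIEF) questionnaires", and the CPT-3 was also taken; no CGI rating is listed there. The CGI-I appears only with the follow-up assessment: "The Clinical Global Impression-Improvement (CGI-I) rating scale was administered by a clinician".

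**The concern.** A paired t-test needs two measurements per participant, and the CGI-I supplies one. Read literally, the plan leaves a listed secondary endpoint without a summary, a null value, a responder cut-off or a test. It is also the only listed efficacy endpoint rated by a clinician; the other five come from parent questionnaires.

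Several analyses are open to the analyst: a test of the ratings against 4, the share rated 1 or 2, or the share rated 1 to 3. If these can point in different directions, and nothing fixes the choice before the ratings are seen, the most favourable one could be reported. In an open-label study with only one group described, a reader would find that hard to detect.

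**Working it through.** **Coverage.** The documents list four primary endpoints (ADHD-RS total, ADHD-RS inattention, ADHD-RS hyperactivity-impulsivity, BRIEF Metacognitive Index) and two secondary ones (BRIEF Global Executive Composite, CGI-I). All except the CGI-I have both a baseline and a 2-month value. So 5 of 6 are covered by the named test, and 1 of 6 (1 of 2 secondary) is not. The CPT-3 is not a listed endpoint and is left out of this count.

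**Assumed N.** The documents state no number of participants. Their inputs are d = 0.5, two-sided alpha 0.05 and power 80%.
- Normal approximation: ((1.960 + 0.842)/0.5)² = 31.4, so 32.
- Exact noncentral t: power 0.795 at 33 and 0.808 at 34, so 34.

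N = 32 to 34 is used below, as an assumption.

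**How far can the summaries diverge?** Take a boundary case, not a forecast: k participants rated 3 and the other N − k rated 4.
- One-sample t-test against 4: |t| = √[(N − 1)k/(N − k)].
- Exact signed-rank test with ratings of 4 dropped: p = 2 × 0.5^k, whatever N is.
- Tie-corrected normal approximation to the signed-rank test, without continuity correction: all k ranks equal (k + 1)/2, so z = [k(k + 1)/4]/[√k (k + 1)/4] = √k.

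| k | t-test against 4 | exact signed-rank | approximate signed-rank |
|---|---|---|---|
| 4 | N = 34: √(33×4/30) = 2.098, p = 0.044; N = 32: √(31×4/28) = 2.104, p = 0.044 | 2 × 0.5⁴ = 0.125 | z = 2, p = 0.0455 (0.072 with continuity correction) |
| 5 | p = 0.023 | 0.0625 | 0.025 (0.037 with continuity correction) |
| 6 | p = 0.012 | 0.031 | not needed; the other two agree |

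At k = 4 the share rated 1 to 3 is 4/34 = 11.8% or 4/32 = 12.5%. The share rated 1 or 2 is 0% for every k, with an exact 95% upper limit of 10.3% (0/34) or 10.9% (0/32).

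**What the table shows.** At k = 4 the t-test and the exact signed-rank test fall on opposite sides of 0.05, but the uncorrected approximate signed-rank test sides with the t-test. Much of the split therefore comes from having only four non-zero differences and from how the p-value is computed. By k = 6 the t-test and the exact test agree. The case is also a corner: the mean is 4 − 4/34 = 3.88, and the standardised shift is 2.098/√34 = 0.36 (0.37 at N = 32), below the 0.5 the study was sized for.

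**Two further invented distributions, N = 34.**
- A: 4 rated 2, 18 rated 3, 12 rated 4. The mean is 3.24 and the t-test against 4 gives p < 0.0001. The share rated 1 or 2 is 4/34 = 11.8%; the share rated 1 to 3 is 22/34 = 64.7%.
- B: 6 rated 1, 8 rated 2, 6 rated 4, 6 rated 5, 6 rated 6, 2 rated 7. The mean is 3.71 and the t-test gives p = 0.40. The share rated 1 or 2 is 14/34 = 41.2%, and the share rated 5 to 7 is also (6 + 6 + 2)/34 = 41.2%.

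A looks better on the mean and B on the top two categories. The seven counts explain both: A is mostly minimal improvement, and B has as many participants worse as better. Each summary can be recomputed from those counts, so a table of them removes the ambiguity.

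**The case for a change.** The best case for a change is that it would cost one sentence, with no new data or visits. The exploratory label is the plan's reason for not adjusting for multiplicity; it does not supply a missing analysis. Distributions A and B show that the choice of summary can alter the impression given, and B needs no exact-versus-approximate subtlety to do so. It might be answered that category 4 implies a test against 4, which is the same arithmetic as pairing each rating with a constant. But the plan does not say this, and it would still leave open whether a t-test or a rank test is meant.

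The omission itself stands, as does the point that different summaries answer different questions. What does not stand is the step to a defect. A significant mean shift and an empty top two categories can both be true of the same ratings: a few participants improved minimally. The contrasts rest on constructed data, one set strongly bimodal. Any particular cut-off would be a reviewer's preference, because the documents define the labels but not which of them count as response. Parts of the document also describe the study in the past tense. If the ratings had already been seen, a sentence added now could not restore prespecification and would serve only as a label.

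**Conclusion.** The plan states no analysis for the CGI-I. This is a minor gap in reporting detail, limited to 1 of 6 listed efficacy endpoints, and it calls for no change. No stated rule yields a wrong result. The paired test covers all four primary endpoints and the other secondary one. The sample size rests on a within-subject effect, and no decision depends on the CGI-I. An analyst would ordinarily tabulate the seven categories with the number missing and name any cut-off or test used; a reader can then check the claim.

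The p-values assume N = 32 to 34 and invented ratings. They show what is possible, not what is likely. The coverage count and the reading of the plan do not depend on them. When the results are read, a CGI-I responder share or p-value given without the category counts should be treated as a choice the plan did not fix in advance.
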